ATTACHMENT 1 – CRF PRE TREATMENT

GENERAL HISTORY

Date of Birth	 /  / 
	day month year
Educational qualification	1 . Academic degree or Bachelor's degree 2.. High school diploma or high school degree (4-5 years) 3.. High school diploma or high school degree (2-3 years) 4.. Secondary school diploma/Professional training diploma 5.. Elementary school diploma (3-5 years) 6 . No degree
Marital status	1 . Married/Cohabitant 2 . Widower 3 . Separated/divorced 4 . Unmarried
Job status	1 . Employed 2 . Unemployed or job quest 3 . Retiree 4 . Never worked
Contact people	1 . Wife, cohabitant Phone number 2.. Daughter/son Phone number 3.. Daughter-in-law /son-in-law Phone number 4.. Other, specify _____ Phone number

Weight	 .  kg	
Smoke	1 .No	
	2.. Yes, in the past, no more now	
	3.. Yes	
Hemoglobin (from blood tests reported in the last 6 months)	 .  g/dl	Blood tests date  /  /  -  day month year

CUMULATIVE ILLNESS RATING SCALE (CIRS)

(Conwell Y et al, 1993)

Indicate for each apparatus the score that best expresses the degree of injury. For diseases that produce lesions in more than one apparatus all present lesions must be reported. For example, an acute cerebrovascular accident (stroke) can damage neurological, vascular, musculoskeletal apparatus and skin at the same time. A metastasized tumor has to be reported either at the apparatus site of the primary tumor or at the vascular system, indicating the extent of the lymph node involvement. If an apparatus is affected by more diseases, the total damage resulted from various diseases must be reported.

For each apparatus the score is so allocated:

1 = ABSENT: "no injuries of an organ / apparatus".

2 = MILD: "the damage does not interfere with the normal activities; therapy is not necessarily required; the prognosis is favorable (eg. hernias, hemorrhoids). "

3 = MODERATE: "the lesion interferes with normal life activities; therapy is required; the prognosis is good (eg. stones, diabetes, fractures). "

4 = SERIOUS: "The injury is debilitating; urgent treatment is required; the prognosis is doubtful (eg. inoperable cancer, emphysema, heart failure)."

5 = VERY SERIOUS: "the injury can be fatal; emergency treatment is required or it is no longer indicated any treatment; the prognosis is severe (eg. myocardial infarction, stroke, intestinal bleeding, embolism). "

	None	Mild	Moderate	Serious	Very serious
1. Cardiac	 1	 2	 3	 4	 5
2. Hypertension (rating is based on severity)	 1	 2	 3	 4	 5
3. Vascular, lymphatics, haematopoietic	 1	 2	 3	 4	 5
4. Respiratory (under the larynx)	 1	 2	 3	 4	 5
5. Eye, ear, nose, throat, larynx	 1	 2	 3	 4	 5
6. Upper gastro-intestinal	 1	 2	 3	 4	 5
7. Lower GI (intestines, hernias)	 1	 2	 3	 4	 5
8. Hepatic (liver only)	 1	 2	 3	 4	 5
9. Renal (kidneys only)	 1	 2	 3	 4	 5
10. Genito-urinary (ureter,-genitals)	 1	 2	 3	 4	 5
11. Musculoskeletal and - integumentary	 1	 2	 3	 4	 5
12. Neurological (except dementia)	 1	 2	 3	 4	 5
13. Endocrine- metabolic, infections, toxicity	 1	 2	 3	 4	 5

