Rationale	
Open questions are still needed to be answered:
 
 - In the exclusive radiotherapy scenario, does ENI produce an overall or biochemical relapse free survival advantage over prostate only radiotherapy for intermediate/high/very high-risk cases? - If ADT is added to prostate only radiotherapy, in intermediate/high/very high-risk cases, ENI is any longer needed?

	
 - Is ENI, associated or not to ADT, linked with an OS or bRFS survival advantage in patients submitted to adjuvant postsurgical prostate radiotherapy? - Additional toxicity due to the larger volumes treated might be reduced by more sophisticated radiotherapy techniques when ENI is added to prostate? - How many Radiation Oncology centers use ENI to treat patients with intermediate/high/very high-risk prostate cancer, with or without ADT? - The data obtained from the present observational study will be helpful for designing a subsequent randomized controlled trial.
End-points	
Primary:
 
 - Overall survival; 
Secondary:
 
 - Cause-specific (CSS) and Biochemical Relapse Free survival (bRFS); - acute and late toxicity evaluation (rectal, bladder, bowel toxicity, according to CTCAE v.4 scale); - Quality of Life deterioration (according to the UCLA-PCI scale).
Study design	
This is a prospective, multicenter, observational cohort study aimed to describe the advantage/disadvantage of different treatments of patients with intermediate/high/very high risk prostate cancer, through a web-based database.
 
The study will include all consecutive patients affected by intermediate, high or very high-risk prostate cancer that fit to the inclusion criteria and who are evaluated at each Centre involved in the study. Patients may have already undergone or not to radical prostatectomy and/or pelvic lymphadenectomy.
 
Phase 1: Establishment of the network of Centers involved in the study Phase 2: Activation and recruitment of eligible cases Phase 3: Follow-up (1,3,6,12/18,24/30/36 months)

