Centers involved will identify all the eligible cases with biopsy proven prostate adenocarcinoma. Patients who are candidate to get involved in the study will be contacted by the physician in charge of the study for each Center. **Every** prostate cancer patient consecutively evaluated at the recruiting Centers and planned to receive radical exclusive or post-operative radiotherapy will be registered; this registration includes demographic and staging results data; only intermediate, high, very high patients will have, however, treatment and follow up CRF compiled (both treated with or without ENI; +/- ADT).

Eligible patients will then receive all the information necessary to formulate their adhesion to the study and finally the physician will fill in the “Pretreatment” Case Report Form (CRF) that will include:

- Demographic Information (date of birth, study title, civil state, working information);
- Another person (relatives, friends,...) as a contact to minimize follow up loss;
- Anamnestic data (height, weight, smoking habit, comorbidities, Cumulative Illness Rating Scale [44], Attachment 1);
- Initial diagnosis (date; PSA at diagnosis);
- Risk factors;
- Staging (clinical TNM, date of biopsy, Gleason score, total number of samples, number of positive samples);
- Quality of life and symptoms caused by prostate cancer (using Italian UCLA Prostate Cancer Index) [45, 46];
- General quality of life (SF-12 Standard V1) [47].

The choice of the treatment will be done based on commonly used international guidelines and on the specific internal protocol of each participating Center.

Since this study is observational, involved patients will be treated following *good clinical practice* and institutional policies procedures.

Clinical outcomes, (such as overall survival and biochemical relapse free survival) and variables, demographic features, dosimetric analysis and acute/late toxicities of both RT and ADT will be reported.

Phase 3: Follow-up (1, 3, 6, 12, 18, 24, 30, 36 months)

After the end of the radiotherapy treatment patients will be evaluated 1, 3, 6, 12, 18, 24, 30 and 36 months since the last session.

Every patient will be contacted by the physicians to fill a CRF that will include:

- Vital state (mortality, date and causes of death) or loss to follow up;
- Last PSA value;

- Other treatments (drugs);

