- Treatment : type of treatment, start date, PSA value before treatment; if surgery type of surgery and pathological TNM, margins, Gleason Score, number of positive lymph nodes; if external RT (intent, modality, technique, dose/fraction, volumes, concomitant hormonal therapies); if brachytherapy (type, intent, dose); if hormone therapy (type of drugs, start and end date, total duration);
- Acute and late toxicities;
- Biochemical Relapse with PSA value and date of last PSA;
- Quality of life and symptoms due to prostate cancer (Italian UCLA-PCI);
- General quality of life SF-12.

Toxicity and response evaluation

The enrolled patients will undergo the first follow up visit one month after the end of radiotherapy. On that occasion, clinical examination will be performed and previously prescribed blood tests, if required, will be evaluated. Genitourinary and gastrointestinal toxicity due to radiation therapy for prostate cancer will be reported according to the NCI Common Terminology Criteria for Adverse Events (CTCAE) version 4 for adverse event (AE) reporting. The CTCAE version 4 is identified and located on the CTEP web site at:

http://ctep.cancer.gov/protocolDevelopment/electronic_applications/ctc.htm [48]

In addition, a Case Report Form (CRF) will be completed (see Attachment 2), regarding:

- Technical characteristics of the radiation treatment (dose, volume, technique, association or not with hormonal therapy);
- Quality of life and complications due to prostate cancer (according to Italian UCLA-PCI) [45, 46];
- General quality of life (SF-12 Standard V1) [47].

Thereafter patients will be evaluated at 3-months, 6-months and 12-months after the end of radiotherapy, and then every 6 months for at least 24 months. During all those scheduled follow up visits, PSA level (jointly with testosterone, in case of association with hormonal therapy) and

previously prescribed blood texts if required, will be evaluated. Patients will undergo clinical examination, and genitourinary and gastrointestinal toxicity will be assessed according to the CTCAE v4.0 classification scale). In addition, a CRF (see Attachment 3) will be completed at each visit, regarding:

- Survival status (mortality, date and cause of death) or exit from the study;
- If macroscopical recurrence or disease progression occurred, the radiological exams (if performed);
- Further treatments received/planned after radiotherapy;
- The last available PSA;

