
select (1=G0, 2=G1, 3=G2, 4=G3, 5=G4, 6=Unknown)

Date yyyy-mm-dd

Urinary Acute Toxicity

select (1=G0, 2=G1, 3=G2, 4=G3, 5=G4, 6=Unknown)

Date

Late Toxicity bladder/ rectum

select (1=Yes, 2=No, 3=Unknown)

Date yyyy-mm-dd

Proctitis

select (1=G0, 2=G1, 3=G2, 4=G3, 5=G4, 6=I Unknown)

Date yyyy-mm-dd

Cystitis

select (1=G0, 2=G1, 3=G2, 4=G3, 5=G4, 6= Unknown)

Date yyyy-mm-dd

Impotence

select (1=No, 2=Yes pre RT, 3=Yes post RT, 4= Unknown)

Date yyyy-mm-dd

Incontinence

select (1=No, 2=Yes pre RT, 3=Yes post RT, 4=Unknown)

TABLE 1 – Toxicity

RECTAL/SMALL BOWEL Acute TOX

G0: No Toxicity

G1: Increased alvus frequency not requiring any treatment. Rectal pain or abdominal pain not requiring any painkillers

G2: Diarrhoea, mucositis, rectal pain or abdominal pain requiring painkillers

G3: Diarrhoea requiring parenteral supportive care, severe mucositis or haematological alterations requiring treatment. Abdominal distension

G4: Acute or subacute obstruction, fistula or perforation, haemorrhage requiring blood transfusion. Abdominal pain or tenesmus requiring ileostomy

BLADDER Acute TOX

G0: No Toxicity

G1: Low urinary tract symptoms (LUTS) and dysuria not requiring any treatment

G2: LUTS, dysuria and urgency requiring treatment or anaesthetics

G3: Severe LUTS, urgency, dysuria, pelvic pain or bladder spasms and haematuria

G4: Haematuria requiring blood transfusion, urinary obstruction, ulceration and necrosis

Late TOX PROCTITIS

G0: No Toxicity

G1: Mild rectal pain, Slight diarrhoea (less than 5 discharges). Small bleeding

G2: Diarrhoea (more than 5 discharges). Significant mucosal secretions and intermittent rectal bleeding

G3: Obstruction or haemorrhage requiring surgery

G4: Necrosis, perforation or fistula

Late TOX CYSTITIS

G0: No Toxicity

G1: Slight epithelial atrophy, small telangiectasia, microscopic haematuria

G2: Moderate LUTS, Intermittent macroscopic haematuria

G3: Severe LUTS and dysuria spread of telangiectasia. Frequent haematuria. Reduction in bladder capacity (less than 150 cc)

G4: Necrosis, bladder capacity reduced (less than 100 cc). Severe haemorrhagic cystitis

SF-12 STANDARD ITALIAN VERSION

(Apolone G et al. 2001)

	Excellent	Very good	Good	Fair	Poor
1 In general, you would say that your health condition is:	1	2	3	4	5
The following questions regard some activities you might do during a typical day. Does your health condition actually limit you in doing these activities?					

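### No rectal, bowel or urinary toxicity grade is taken before radiotherapy and no rule uses the other baseline data, so some existing symptoms may be recorded as radiation toxicity

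*Combined protocol and SAP*

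**What the plan says.** The synopsis lists as a secondary endpoint "acute and late toxicity evaluation (rectal, bladder, bowel toxicity, according to CTCAE v.4 scale"). The section on toxicity and response evaluation adds an attribution: "Genitourinary and gastrointestinal toxicity due to radiation therapy for prostate cancer will be reported according to the NCI Common Terminology Criteria for Adverse Events". It also sets the first assessment after treatment: "The enrolled patients will undergo the first follow up visit one month after the end of radiotherapy".

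Grades are entered on the follow-up forms. Attachments 2 and 3 carry rectal, small-bowel and urinary acute grades and late proctitis and cystitis grades, coded "select (1=G0, 2=G1, 3=G2, 4=G3, 5=G4, 6=Unknown"). Table 1 in the same attachments gives the grade definitions. Impotence is coded differently, "select (1=No, 2=Yes pre RT, 3=Yes post RT, 4= Unknown"), and incontinence has the same before/after options. No other toxicity item does.

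Before treatment, the plan collects "Quality of life and symptoms caused by prostate cancer (using Italian UCLA Prostate Cancer Index"), together with the SF-12 and the CIRS. The form that does this, "ATTACHMENT 1 – CRF PRE TREATMENT", has no G0 to G4 field.

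The Statistical Analyses section names chi-squared or Fisher tests for associations between categorical variables. It mentions possible confounders only for regression on survival. It gives no rule for baseline symptoms in the toxicity analysis.

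**The concern.** The endpoint is toxicity caused by radiotherapy, but the grade records what the patient has on the day. A man with untreated lower urinary tract symptoms (LUTS) and dysuria before the first fraction who is unchanged at one month meets the Table 1 definition of acute bladder grade 1. Nothing on the endpoint's own scale shows that he met it beforehand.

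The cohort mixes unoperated men with men irradiated after prostatectomy. The background section itself names urinary incontinence and persistent bleeding as severe post-surgical side effects. Incontinence has a before/after code; bleeding has none.

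The toxicity data serve comparisons. Aim 5 sets toxicity in clinical and therapeutic subgroups against historical data, and one rationale question asks about the added toxicity of elective nodal irradiation (ENI). If baseline symptoms differ between the groups compared, part of a difference in recorded toxicity may have been there before treatment.

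**Working it through.** **Step 1. What each form records.** The plan states no toxicity rate or precision, so there is no figure of its own to reproduce on this point. The check begins with the forms.

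| Symptom used in Table 1 | Where it drives a grade | Asked at baseline in Attachment 1? |
|---|---|---|
| LUTS, dysuria, bladder urgency | Acute bladder G1 to G3; LUTS and dysuria also in late cystitis | No. UCLA-PCI urinary items cover leakage, control, pads and bother |
| Haematuria | Acute bladder G3 and G4, late cystitis G1 to G3 | No |
| Diarrhoea | Acute rectal/small bowel G2 and G3, late proctitis G1 and G2 | No. UCLA-PCI bowel items cover rectal urgency, distress, cramps and bother |
| Rectal bleeding | Late proctitis G1 and G2 | No |
| Abdominal pain | Acute rectal/small bowel G1 and G2 | Partly, through the item on cramps |
| Incontinence, impotence | Separate items, not part of the Table 1 grades | Yes in UCLA-PCI, and coded before/after RT at follow-up |

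The CIRS adds one score from 1 to 5 for lower GI and one for genito-urinary disease. These are organ-level comorbidity scores and do not identify the symptoms in the table.

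**Step 2. What can be computed.** Change from baseline in a rectal, bowel, urinary, proctitis or cystitis grade needs that grade before and after treatment. Only the second is collected.

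**Step 3. Illustrative size.** All inputs here are assumptions:
- b, the share with a grade 1 or worse symptom before radiotherapy: 10% to 30%.
- t, the share of the remaining men in whom radiotherapy causes such a symptom: 20%.
- f, the share of men with existing symptoms who are graded as having radiation toxicity: 0 to 1. Existing symptoms are taken neither to resolve nor to worsen.

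Crude recorded rate = f × b + (1 − b) × t. New-symptom rate over the whole cohort = (1 − b) × t.

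| b | New rate (f = 0) | Recorded, f = 0.5 | Recorded, f = 1 |
|---|---|---|---|
| 10% | 0.90 × 0.20 = 18% | 5% + 18% = 23% | 10% + 18% = 28% |
| 20% | 0.80 × 0.20 = 16% | 10% + 16% = 26% | 20% + 16% = 36% |
| 30% | 0.70 × 0.20 = 14% | 15% + 14% = 29% | 30% + 14% = 44% |

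The last column is the upper bound for each b. The recorded rate should be compared with 18% to 14%, not with 20%, because t applies only to men free of symptoms beforehand.

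**Step 4. Two groups with the same t.** Take one group with b = 10% and another with b = 30%. The recorded difference is 44% − 28% = 16 points at f = 1 and 29% − 23% = 6 points at f = 0.5. With perfect attribution it is 14% − 18% = −4 points, because fewer men in the second group can develop a new symptom. The gap depends on the assumed baseline imbalance and on f, and the documents give neither.

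**The case against.** The strongest reply is that the baseline is not empty. Attachment 1 has physician-scored CIRS items for lower GI and genito-urinary disease, and UCLA-PCI urinary and bowel items. Investigators are asked for toxicity due to radiotherapy, so they are expected to discount what was there before. Incontinence, the urinary after-effect of surgery that the protocol names, is coded separately and is not among the Table 1 bladder symptoms. Treatment setting, surgery and pathology are recorded, so analyses can be stratified, and the ENI survival questions are already posed separately for the exclusive and adjuvant settings.

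Most of this stands, and it limits what can be claimed. A reader might infer:
- That existing symptoms will all be counted as toxicity. The attribution wording and the before/after codes do not support that.
- That post-prostatectomy symptoms are common in this cohort. The documents give no frequency, and they describe follow-up with later salvage treatment as an alternative for men with severe after-effects.
- That ENI comparisons are biased. That would require baseline symptoms to differ by ENI use within setting, which nothing in the documents shows.
- That quality of life has the same defect. It does not: UCLA-PCI and SF-12 are collected before and after treatment on the same scale.

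The reply does not supply a reference grade. Attribution is left to a judgement made at follow-up with no recorded pre-treatment grade to check it against. The baseline instruments omit dysuria, haematuria, rectal bleeding and diarrhoea, and the plan does not say that they will be used in the toxicity analysis.

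**Conclusion.** The point holds in a limited form. Rectal, small-bowel, urinary, proctitis and cystitis grades have no pre-treatment value on their own scale, and no rule ties the baseline UCLA-PCI or CIRS scores to the toxicity analysis. Symptoms such as LUTS, dysuria, haematuria, rectal bleeding and diarrhoea that predate radiotherapy may be recorded as toxicity, and contrasts between subgroups with different baseline symptoms may be biased.

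The size is not derivable from the documents. The illustration gives a ceiling, not an expectation. Its inputs (b, t, and every existing symptom graded as toxicity) are all assumed, and the 16-point contrast also assumes a 10% against 30% imbalance. It would be wrong to read 28% to 44% as forecast rates.

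This is worth correcting, though not critical. Toxicity is a secondary endpoint and partial proxies exist, but a missing pre-treatment grade cannot be reliably reconstructed once treatment has started.

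**What to change.** 1. Add to Attachment 1 the same rectal, small-bowel and urinary grade items used at follow-up, plus proctitis and cystitis, scored before the first fraction. The three acute items alone would not serve late toxicity, which has its own scales. Some late criteria, such as telangiectasia and bladder capacity, may not be known beforehand, so keep the existing code for unknown.
2. In the statistical section, define toxicity as a new grade or one worse than baseline, and report the crude grade beside it.
3. Adjust toxicity comparisons for the matching baseline UCLA-PCI domain (urinary or bowel), which is already collected. For any men already enrolled this is the only remedy. It is partial, because the index omits several of the symptoms that set the grades.

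The cost is about five extra fields at a visit that already takes place, a few lines of analysis text and slightly more analysis.

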	2 . Yes, monolateral
	3 . Yes, bilateral
Pathological TNM after surgery	T __ N __ M __
Margins	1 R0
	2 R1
	3 R2
Gleason Score after surgery	__ + __ = __
Pre-treatment PSA __ ng/mL	
PSA date	__ / __ / __ day month year

SF-12 STANDARD ITALIAN VERSION

(Apolone G et al. 2001)

	Excellent	Very good	Good	Fair	Poor
1 In general, you would say that your health condition is:	1	2	3	4	5
The following questions regard some activities you might do during a typical day. Does your health condition actually limit you in doing these activities?					
	Yes, it limits a lot	Yes, it limits a little	No, it does not limit at all		
2 Activities of moderate physical effort , such as moving a table , using the vacuum cleaner , playing bowls or a riding a bicycle	1	2	3		
3 Climbing several flights of stairs	1	2	3		
During the last 4 weeks have you had the following problems at work or during other daily activities, because of your physical health condition?					
	Yes	No			
4 Accomplished less than you would like	1	2			
5 You had to limit certain kinds of occupation or other activities	1	2			
During the last 4 weeks have you had the following problems at work or during other daily activities, because of your emotional state (such as feeling depressed or anxious)?					
	Yes	No			
6 Accomplished less than you would like	1	2			
7 You did not do work or other activities as carefully as usual	1	2			
	Not at all	A little bit	Moderately	Quite a bit	Not at all
8 During the last 4 weeks , How much has pain hindered your usual work (at home and outside)?	1	2	3	4	5
How long during the last 4 weeks have you felt					
	All of the time	Most of the time	A good bit of time	Some of the time	A little of the time
9 calm and serene?	1	2	3	4	5
10 full of energy?	1	2	3	4	5
11 discouraged and sad	1	2	3	4	5
	All of the time	Most of the time	A good bit of time	Some of the time	A little of the time
12 During the last 4 weeks , how long have your physical health condition or your emotional state interfered with your social activities, with family, with friends?	1	2	3	4	5

COMPLICATIONS DUE TO PROSTATE CANCER
ITALIAN UCLA PROSTATE CANCER INDEX
(Gacci M et al, 2005)

URINARY FUNCTION

This session regards the urinary routine. Please consider only the last 4 weeks.

1. Over the LAST 4 WEEKS, how often have you leaked urine?
 - 1 Every day.
 - 2 About once a week
 - 3 Less than once a week
 - 4 Not at all.
2. Which of the following best describes your urinary control during the LAST 4 WEEKS?
 - 1 No control whatsoever
 - 2 Frequent dribbling
 - 3 Occasional dribbling
 - 4 Total control
3. How many pads or adult diapers per day have you usually used to control leakage during the LAST 4 WEEKS?
 - 1 3 or more pads per day
 - 2 1-2 pads per day
 - 3 No pads
4. How big a problem, if any, has each of the following been for you?
Dripping urine or wetting your pants?
 - 0 No problem
 - 1 Very small problem
 - 2 Small problem
 - 3 Moderate problem
 - 4 Big problem
Urine leakage interfering with your sexual activity?
 - 0 No problem
 - 1 Very small problem
 - 2 Small problem
 - 3 Moderate problem
 - 4 Big problem
5. Overall, how big a problem has your urinary function been for you during the LAST 4 WEEKS?
 - 0 No problem
 - 1 Very small problem
 - 2 Small problem
 - 3 Moderate problem
 - 4 Big problem

BOWEL FUNCTION

The following section talks about all the bowel function and abdominal pain. Please consider only the last 4 weeks.

6. How often have you had rectal urgency (felt like you had to pass stool, but did not) during the LAST 4 WEEKS?
 - 1 More than once a day
 - 2 About once a day
 - 3 More than once a week
 - 4 About once a week
 - 5 Rarely or never
7. How much distress have your bowel movements caused you during the LAST 4 WEEKS?
 - 1 Severe distress

2 Moderate distress
 3 A little distress
 4 No distress

8. How often have you had crampy pain in your abdomen or pelvis during the LAST 4 WEEKS?
 1 Several times a day
 2 About once a day
 3 Several times a week
 4 About once this month
 5 Rarely or never

9. In particular, how big was the problem of bowel habits during the LAST 4 WEEKS?
 1 Big problem
 2 Moderate problem
 3 Little problem
 4 Very small problem
 5 No problem

SEXUAL FUNCTION

THE NEXT SECTION IS ABOUT YOUR SEXUAL FUNCTION AND SEXUAL SATISFACTION. MANY OF THE QUESTIONS ARE VERY PERSONAL, BUT THEY WILL HELP US UNDERSTAND THE IMPORTANT ISSUES THAT YOU FACE EVERY DAY. REMEMBER THAT YOUR ANSWERS TO THIS QUESTIONNAIRE WILL BE KEPT CONFIDENTIAL AND WILL BE USED ONLY FOR RESEARCH PURPOSES. PLEASE ANSWER HONESTLY ABOUT THE LAST 4 WEEKS ONLY.

10. HOW WOULD YOU RATE EACH OF THE FOLLOWING DURING THE LAST 4 WEEKS?

	Very poor	Poor	Fair	Good	Very good
A. Your ability to have an erection?	1	2	3	4	5
B. Your ability to reach orgasm (climax)	1	2	3	4	5

11. How would you describe the usual QUALITY of your erections?
 1 None at all
 2 Not firm enough for any sexual activity
 3 Firm enough for masturbation and foreplay only
 4 Firm enough for intercourse

12. How would you describe the FREQUENCY of your erections?
 1 I NEVER had an erection when I wanted one
 2 I had an erection LESS THAN HALF the time I wanted one
 3 I had an erection ABOUT HALF the time I wanted one
 4 I had an erection MORE THAN HALF the time I wanted one
 5 I had an erection WHENEVER I wanted one

13. Overall, how would you rate your sexual function during the LAST 4 WEEKS?
 1 Very poor
 2 Poor
 3 Fair
 4 Good
 5 Very good

14. Overall, how big a problem has your sexual function been for you during the LAST 4 WEEKS?
 1 No problem
 2 Very small problem
 3 Small problem
 4 Moderate problem
 5 Big problem

